# 11.4. Independent Ethical Committee (IEC) or Institutional Review Board (IRB) Review

Prior to commencement of the trial at a given site, this clinical trial protocol will be submitted together with its associated documents to the Central IEC for its favourable opinion, which will be filed in the Investigator Site File. A copy will be filed in the Sponsor Trial Master File.

The IEC will be asked to document the date of the meeting at which the favourable opinion or approval was given and the members and voting members present. Written evidence of favourable opinion or approval that clearly identifies the trial, the clinical trial protocol version and the Subject Information and Informed Consent Form version reviewed should be provided.

Amendments to this clinical trial protocol will also be submitted to the concerned IEC or IRB, before implementation of substantial changes. Relevant safety information will be submitted to the IEC during the course of the trial in accordance with national regulations and requirements.

Initial IEC positive vote, and all materials approved by the IEC for this study including the patient consent form and recruitment materials must be maintained by the Investigator and made available for inspection.

#### 11.5. Ethical Conduct of the Study

The study will be performed in accordance with ethical principles that have their origin in the Declaration of Helsinki and are consistent with ICH/Good Clinical Practice, applicable regulatory requirements.

#### 11.6. Written Informed Consent

The Principal Investigator(s) at each centre will ensure that the patient is given full and adequate oral and written information about the nature, purpose, possible risk and benefit of the study. Patients must also be notified that they are free to discontinue from the study at any time. The patient should be given the opportunity to ask questions and allowed time to consider the

information provided. The patient's signed and dated informed consent must be obtained before conducting any study procedures.
The Principal Investigator(s) will retain the original, signed ICF; this form will be made available for reviewing during monitoring visits. A copy of the signed ICF will be provided to the patient. The Principal Investigator will document the informed consent procedure in the patient medical records.

12. QUALITY CONTROL AND QUALITY ASSURANCE	
To ensure compliance with Good Clinical Practices and all applicable regulatory requirements, t Sponsor may conduct a quality assurance audit.	he

#### 13. Data handling and record keeping

The data will be recorded using the Electronic Data Capture software property of which is developed and maintained with strict observance of the regulatory standards for Clinical EDC systems, with special observance of the guidelines specified at:

- CPMP/ICH/135/95. ICH E6. Note for Guidance on Good Clinical Practice.
- Good Clinical Data Management Practice, Version 4, Society for Clinical Data Management (SCDM), October 2005.
- EMEA. Reflection on expectations for electronic source documents used in clinical trials. London, 17 October 2007.
- Directive 9 Guidance for Industry. Part 11, Electronic Records; Electronic Signatures Scope and Application (August 2003).
- FDA. Guidance for Industry. Computerized Systems Used in Clinical Investigations (May 2007).
- FDA. Guidance for Industry. Part 11, Electronic Records; Electronic Signatures Scope and Application (August 2003)

All the EDC users are uniquely identified by name, all the access to the software are made through a secure, encrypted connection and all the activity is logged and audited.

All the EDC forms are built according to the CRF defined by the study protocol and is validated according the DVP (Data Validation Plan) associated.

#### 13.1. Inspection of Records

The Sponsor will be allowed to conduct site visits to the investigation facilities for the purpose of monitoring any aspect of the study. The Investigator agrees to allow the monitor to inspect the drug storage area, study drug stocks, drug accountability records, subject charts and study source documents, and other records relative to study conduct.

#### 13.2. Retention of Records

Upon initiation of the trial, the Investigator will be provided with an Investigator Site File containing all necessary trial documents, which will be completed throughout the trial and updated as necessary. The file must be available for review by the Monitor during Sponsor audits, and for inspection by Health Authorities during and after the trial. Moreover, the file must be safely archived for at least 25 years (as per local requirements) after the end of the trial. The documents to be archived include the Subject Identification List and the signed subject Informed Consent Forms. If archiving of the Investigator Site File is no longer possible at the site, the Investigator must notify the Sponsor/designee.

All original subject files (medical records) must be stored at the site (hospital, research institution, or practice) for the longest possible time permitted by the applicable regulations, and/or as per ICH GCP guidelines, whichever is longer (In Spain 25 years). In any case, the Investigator should ensure that no destruction of medical records is performed without the written approval of the Sponsor.

#### 14. Publication Policy

As stated in article 42 of RD 1090/2015 of clinical trials, the Sponsor is obliged to publish both positive and negative results of the authorized clinical trials in scientific journals and with mention to the Ethical Committee of Clinical Research that approved the study.

After completion of the trial, the clinical publication will be carried out by the Coordinating Investigator in collaboration and Principal Investigators, however interim analysis of preliminary data of primary/secondary endpoints may be published by the Sponsor in scientific meetings and/or Congresses. The order of authors will strictly depend on the number of eligible patients included by the Investigators. Coordinating investigators will be first and last authors, and the number of the rest of the authors will depend on the above rule and the requirements of the congresses and/or journals.

The results will be published in two publications. It is estimated that the first publication will include the results of the analysis of the primary/secondary endpoints and will include data from the symptomatic cohort. The second publication will include the results of the analysis of the primary/secondary endpoints from the asymptomatic cohort and potential comparisons between both cohorts. The Investigator will inform the Sponsor in advance about any plans to publish or present data from the trial. Any publications and presentations of the results (abstracts in journals or newspapers, oral presentations, etc.), either in whole or in part, by Investigators or their representatives will require written authorization by the Sponsor before submission.

The anonymity of the source subjects of the data and biological samples will be maintained at all times. The results or conclusions of the study will be communicated primarily in scientific publications before being released to the non-health public. No efficacy study outcome will be reported prematurely or in a sensationalistic way. Participating investigators should not publish any patient data that is directly related to the study objectives until the trial report is published.

The trial will be registered in the Spanish Registry of Clinical Studies (REEC - Registro Español de Estudios Clínicos) and Clinical trials.gov before including the first patient.

# EORTC QLQ-C30 (versión 3)

Estamos interesados en conocer algunas cosas sobre usted y su salud. Por favor, responda a todas las preguntas personalmente, rodeando con un círculo el número que mejor se aplique a su caso. No hay contestaciones "acertadas" o "desacertadas". La información que nos proporcione será estrictamente confidencial.

Por favor ponga sus iniciales:				
Su fecha de nacimiento (día, mes, año):				
Fecha de hoy (día, mes, año): 31				
	En absoluto	Un poco	Bastante	Mucho
1. ¿Tiene alguna dificultad para hacer actividades que requierea un esfuerzo importante, como llevar una bolsa de compra pesada o una maleta?	1	2	3	4
2. ¿Tiene alguna dificultad para dar un paseo largo ?	1	2	3	4
3. ¿Tiene alguna dificultad para dar un paseo corto fuera de casa?	1	2	3	4
4. ¿Tiene que permanecer en la cama o sentado/a en una silla durante el día?	1	2	3	4
5. ¿Necesita ayuda para comer, vestirse, asearse o ir al servicio?	1	2	3	4
Durante la semana pasada:	En absolu to	Un poco	Bastante	Mucho
6. ¿Ha tenido algún impedimento para hacer su trabajo u otras actividades cotidianas?	1	2	3	4
7. ¿Ha tenido algún impedimento para realizar sus aficiones u otras actividades de ocio?	1	2	3	Δ

1

2

3

4

8. ¿Tuvo sensación de "falta de aire" o dificultad para respirar?	1	2	3	4
9. ¿Ha tenido dolor?	1	2	3	4
10. ¿Necesitó parar para descansar?	1	2	3	4
11. ¿Ha tenido dificultades para dormir?	1	2	3	4
12. ¿Se ha sentido débil?	1	2	3	4
13. ¿Le ha faltado el apetito?	1	2	3	4
14. ¿Ha tenido náuseas?	1	2	3	4
15. ¿Ha vomitado?	1	2	3	4
16. ¿Ha estado estreñido/a?	1	2	3	4

Por favor, continúe en la página siguiente

Durante la semana pasada:	En absoluto	Un poco	Bastante	Mucho
17. ¿Ha tenido diarrea?	1	2	3	4
18. ¿Estuvo cansado/a?	1	2	3	4
19. ¿Interfirió algún dolor en sus actividades diarias?	1	2	3	4
20. ¿Ha tenido dificultad en concentrarse en cosas como leer el periódico o ver la televisión?	1	2	3	4
21. ¿Se sintió nervioso/a?	1	2	3	4
22. ¿Se sintió preocupado/a?	1	2	3	4
23. ¿Se sintió irritable?	1	2	3	4
24. ¿Se sintió deprimido/a?	1	2	3	4
25. ¿Ha tenido dificultades para recordar cosas?	1	2	3	4
26. ¿Ha interferido su estado físico o el tratamiento médico en su vida familiar?	1	2	3	4
27. ¿Ha interferido su estado físico o el tratamiento médico en sus actividades sociales?	1	2	3	4
28. ¿Le han causado problemas económicos su estado físico o el tratamiento médico?	1	2	3	4

# Por favor en las siguientes preguntas, ponga un círculo en el número del 1 al 7 que mejor se aplique a usted

	23,	SCOIIIO A	a101a11a Su Sa	iuu generai uuran	te la Semana pa	Saua:	
1		2	3	4	5	6	7
Pésii	ma					I	Excelente
	30.	¿Cómo v	aloraría su ca	lidad de vida en g	eneral durante	la semana pasada	a?
1		2	3	4	5	6	7
Pésii	ma					I	Excelente

 $@ \ QLQ-C30 \ Copyright \ 1995 \ EORTC \ Quality \ of \ Life \ Group. \ Reservados \ todos \ los \ derechos. \ Versi\'on \ 3.0$ 

#### Appendix 2:

### ÍNDICE DE BARTHEL MODIFICADO DE ACTIVIDADES BÁSICAS DE LA VIDA DIARIA

*Instrucciones:* Seleccione la puntuación para cada afirmación que más se ajuste al nivel de capacidad actual del paciente para cada uno de los 10 ítems siguientes. Registre la actividad actual, no la potencial. La información puede obtenerse a través del propio paciente, de una persona que esté familiarizada con las capacidades del paciente (como un familiar), o de la observación. Véase el apartado de directrices de la página siguiente para más información sobre la puntuación e interpretación.

#### Control de heces

0 = incontinente (o necesita que le administren enemas)

1 = accidente excepcional (uno/semana)

2 = continente

Puntuación del paciente:

#### Control de orina

0 = incontinente, o sondado e incapaz de cambiarse la bolsa.

1 = accidente excepcional (máximo uno/24 horas).

2 = continente (durante al menos 7 días)

Puntuación del paciente:

#### Aseo personal

0 = necesita ayuda con el aseo personal

1 = independiente para lavarse la cara, las manos y los dientes, y afeitarse (proporcionados los instrumentos)

Puntuación del paciente:

#### Uso del retrete

0 = dependiente

1 = necesita alguna ayuda, pero puede hacer algo solo

2 = independiente (entrar y salir, limpiarse y vestirse)

Puntuación del paciente:

#### Comer

0 = incapaz

1 = necesita ayuda para cortar, extender mantequilla, etc.

2 = independiente (la comida está al alcance de la mano)

Puntuación del paciente:

#### Trasladarse entre la silla y la cama

0 = incapaz, no se mantiene sentado

1 = necesita ayuda importante (una persona o dos personas, física), puede estar sentado

2 = necesita algo de ayuda (física o verbal)

3 = independiente

Puntuación del paciente:

#### **Desplazarse**

0 = inmóvil

1 = independiente en silla de ruedas, incluidas las esquinas, etc.

2 = anda con pequeña ayuda de una persona (física o verbal)

3 = independiente (pero puede usar cualquier tipo de ayuda, p. ej., bastón)

Puntuación del paciente:

#### Vestirse y desvestirse

0 = dependiente

1 = necesita ayuda, pero puede hacerlo a medias

2 = independiente (incluidos botones, cremalleras, cordones, etc.)

Puntuación del paciente:

#### Subir y bajar escaleras

0 = incapaz

1 = necesita ayuda (física o verbal, puede llevar cualquier tipo de muleta)

2 = independiente para subir y bajar

Puntuación del paciente:

#### Bañarse/Ducharse

0 = dependiente

1 = independiente

Puntuación del paciente:

#### Puntuación total:

-----

#### Puntuación:

Sume las puntuaciones del paciente en cada ítem. Las puntuaciones totales posibles oscilan entre 0 y

20, y las puntuaciones más bajas indican un incremento de la incapacidad. Si se utiliza para medir la mejoría después de rehabilitación, los cambios en más de dos puntos en la puntuación total reflejan posible cambios reales, y también es probable un cambio en un ítem de completamente dependiente a independiente.

Directrices para el Índice de Barthel de actividades básicas de la vida diaria

Aspectos generales

- El índice de Barthel se debe utilizar como registro de lo que un paciente hace, NO como registro de lo que el paciente podría hacer.
- El objetivo principal es establecer el grado de independencia del paciente de cualquier tipo de ayuda, física o verbal, por mínima que sea y por cualquier razón.
- La necesidad de supervisión hace al paciente no independiente.
- La funcionalidad del paciente se debe establecer usando la mejor evidencia disponible.

Preguntar al paciente, amigos/familiares y cuidadores será la fuente habitual, pero la

observación directa y el sentido común también son importantes. No obstante, no será necesaria una prueba directa.

- Por lo general, la funcionalidad del paciente durante las 24 48 horas anteriores es importante, pero ocasionalmente serán pertinentes periodos más largos de tiempo.
- A los pacientes con pérdida de conciencia se les puntuará con "0" en todos los ítems, aunque aún no presenten incontinencia.
- Las categoría intermedias implican que el paciente realiza más del 50 % del esfuerzo.
- Está permitido el uso de ayudas para ser independiente.

Control de heces (semana anterior)

- Si fue necesario que el cuidador aplicará un enema, se considera "incontinente".
- «Ocasional» = una vez a la semana.

Control de orina (semana anterior)

- «Ocasional» = menos de una vez al día.
- Un paciente con sonda que pueda manejar completamente la sonda por sí solo se registrará como "continente".

Aseo personal (24 - 48 horas anteriores)

• Se refiere a la higiene personal: lavarse los dientes, colocarse la dentadura postiza, peinarse, afeitarse, lavarse la cara. Los instrumentos los puede proporcionar el cuidador.

Uso del retrete

- Si es capaz de alcanzar el retrete/tapa del retrete, desvestirse de forma suficiente, limpiarse por sí mismo, vestirse y salir.
- "Con ayuda" = puede limpiarse por sí solo y hacer algunas de las tareas indicadas anteriormente

#### Comer

- Capaz de ingerir alimentos normales (no solo alimentos blandos). Alimentos cocinados y servidos un tercero, pero sin cortar.
- «Ayuda» = cortándole la comida, el paciente se alimenta por sí solo.

Trasladarse entre la silla y la cama

- De la cama a la silla y al revés.
- «Dependiente» = NO se mantiene sentado (incapaz de sentarse); se necesitan dos personas para levantarlo.
- "Ayuda importante" = una persona fuerte/entrenada o dos personas normales. Puede sentarse.
- "Ayuda menor" = una persona fácilmente, O necesita supervisión por motivos de seguridad.

Desplazarse

- Hace referencia a la movilidad en la casa o sala, en el interior. Puede usar ayuda. Si está en silla
- de ruedas, puede pasar las esquinas/puertas sin ayuda.
- «Ayuda» = por una persona no entrenada, incluida la supervisión y el apoyo moral.

Vestirse y desvestirse

- Si es capaz de seleccionar y ponerse la ropa, que puede estar adaptada.
- «A medias» = ayuda con los botones, cremalleras, etc. (¡comprobar!), pero puede ponerse alguna prendas por sí solo.

Subir y bajar escaleras

• Puede utilizar cualquier tipo de ayuda para andar para considerarse independiente.

Bañarse/Ducharse

- Por lo general, la actividad más difícil.
- Debe entrar y salir sin supervisión y lavarse por sí solo
- Independiente en la ducha = "independiente" si no necesita supervisión/ayuda.

# 1. TABLE OF CONTENTS

# 2. PATIENT POPULATIONS

#### ITT Population:

The ITT population will include all patients who were included in the study, only screening failures are excluded.

#### PP Population:

The PP population will include all patients who fulfilled the inclusion and exclusion criteria and had at least 2 valid tumor evaluations (baseline + 1st assessment).

#### Safety Population:

The PP population will include all patients who received at least one dose of the treatment.

Table 1: ITT population

Intention to treat population	
No	
Yes	

Table 2: ITT Population: Patients excluded

Patient number	Cohort	ITT	Exclusion reason

Table 3: PP population

PP			
No			
Yes			

Table 4: PP Population: Patients excluded

Patient number	Cohort	PP	PP: exclusion reason

Table 5: Safety population

Safety	
No	
Yes	

Table 6: Safety Populattion: Patients excluded

Patient number	Cohort	Safety	Safety: exclusion reason

Table 7: Analysis populations, all patients

[figure not shown]
Patient Number	Cohort	Intention to treat population	PP	ITT/PP Exclusion reason	Safety	Safety: exclusion reason

[figure not shown]
# 3. RESULTS

# 3.1. RECRUITED PATIENTS

All baseline characteristics will be performed using the ITT and PP population. In order to report the main efficacy analysis, also both the ITT and PP population will be used, meanwhile the secondary efficacy endpoints will be analyzed using the PP population. Finally the safety population will be used to report the safety results.

Table 8: Patients recruited by Hospital

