## 5.3. Patient Inclusion and Cohort Assignment

During the screening (28 days before day 1 cycle 1) it should be assessed whether the patient is symptomatic (cohort 2) or asymptomatic (cohort 1).

Definition of Asymptomatic (cohort 1):.Patients without active symptoms secondary to brain metastases at the moment of inclusion.

After confirming that a patient fulfils all eligibility criteria of the study (inclusion/exclusion criteria), site staff will initiate the eCRF registration procedure.

Once procedure is fulfilled the site staff will receive the "Inclusion confirmation communication", and protocol-specific treatment can be initiated.

This is an open label, single arm study including two cohorts of patients, in each cohort, patients will be treated with encorafenib 450 mg once daily and binimetinib 45 mg twice daily.

After 56 days of treatment, a contrast enhanced brain MRI and CT body scan will be performed as first tumour assessment:

- Patients with PD at first evaluation in brain MRI (modified RECIST 1.1 criteria) and /or body CT scan (RECIST 1.1 criteria) will discontinue study treatment and will continue in the study for OS follow-up.
- Patients with CR in brain (modified RECIST 1.1) and no PD in the body (RECIST 1.1), will continue study treatment and will be followed every two months with contrast enhanced brain MRI and body CT scan up to 12 months. If no PD after one year, patients will be followed as per institutional criteria, and continue with the treatment.
  - o If considered by the investigator, local treatment can be done for brain CR patients, but only after confirming no safety concerns (defined as substantial deterioration of vital signs (including ECOG PS), physical examination, ECG, Lab. Values that do not recommend RT) with the three first patients treated with radiation therapy in the running phase (for more information, please see section 9.1).
- Patients with no CR and no PD in brain MRI per modified RECIST 1.1 criteria, and no PD in body per RECIST 1.1 criteria, will be treated with local RT and/or radiosurgery, and then will continue Enco and Bini. The first 3 patients will be treated in a running

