performed within 6 months after database closure expected at 24 months after last patient inclusion, however interim analysis might be performed when analysing other primary variables

Percentage of patients (%) free of extracraneal progression at 6 (week 24), 12 (week 28) and 24 months (week 96): percentage of patients free of progression by RECIST 1.1 at 6 months (week 24), 12 months (week 48) and 24-month (week 96) considering date of inclusion. The final statistical analysis of this endpoint is expected to be performed within 6 months after database closure expected at 24 months after last patient inclusion, however interim analysis might be performed when analysing other primary variables.

**Overall Survival in both cohorts (OS):** OS is calculated as the time from date of inclusion to date of death due to any cause. The final statistical analysis of this endpoint is expected to be performed within 6 months after database closure expected at 24 months after last patient inclusion, however interim analysis might be performed when analysing other primary variables.

Percentage of patients (%) alive at 6, 12 and 24 months in both cohorts: percentage of patients alive at 6 months, 12 month and 24-month considering date of inclusion. The final statistical analysis of this endpoint is expected to be performed within 6 months after database closure expected at 24 months after last patient inclusion, however interim analysis might be performed when analysing other primary variables.

**Toxicity of the combination until local treatment:** Number of patients with adverse events and serious adverse events, changes in laboratory values, vital signs, electrocardiograms (ECGs), LVEF (MUGA (Multigated Acquisition Scan) / echocardiogram) and assessment of physician, dermatological and ocular examinations graded according to the National Cancer Institute (NCI) Common Terminology Criteria for Adverse Events (CTCAE) v 4.03 until local treatment (local treatment D1). It will be studied using descriptive statistics techniques, such as frequency tables and contingency tables. The final statistical analysis of this endpoint is expected to be performed within 6 months after database closure expected at 24 months after last patient inclusion, however interim analysis might be performed when analysing other primary variables.

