#### 10.5. Definition of study populations

Data of study will be analysed in the following populations:

- 1. ITT: All patients that have been enrolled in the trial.
- 2. Evaluable population per protocol (PP): All patients fulfilling all eligibility criteria and having at least two valid tumour assessments (baseline and one evaluation MRI or CT-scan) without any protocol deviation that makes the patient invalid for the primary endpoint evaluation.
- 3. Safety population: All patients receiving at least one dose of treatment.

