# 4.5. INTRACRANIAL OVERALL SURVIVAL (IOS). 4.5.1.ITT ALL PATIENTS: INTRACRANIAL OVERALL SURVIVAL (IOS).

Table 54: Events type OS

os	N	%	95%CI
Alive			
Death			
Total			

Table 55: Median/mean OS (estimated by Kaplan-Meier)

	Median (months)	CI 95%	Mean	CI 95%
Overall survival				

Table 56: OS estimated survival ratio

os	Events (%, total N)	Patients at risk	% estimated cumulative survival ratio	CI 95%
At 6 months At 12 months At 18 months At 24 months				

Figure 5: Overall survival

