# 4.6. INTRACRANIAL PROGRESSION-FREE SURVIVAL (IPFS).

Intracranial Progression-free survival (PFS), defined as the time from inclusion (first dose of treatment) until intracranial tumour progression (RECIST 1.1) or death. Patients without any of the previous events are censored at the date of the last available tumor assessment.

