### Figure: intracranial Progression Free Survival (PP Cohort 2)

# 4.7. Extracranial Progression-free survival (ePFS).

Extracranial Progression-free survival (PFS), defined as the time from inclusion (first dose of treatment) until extracranial tumour progression (RECIST 1.1) or death. Patients without any of the previous events are censored at the date of the last available tumor assessment.

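### SAP 3.1 assigns secondary efficacy to PP alone, against its own ITT-and-PP survival shells; PP omits patients who die or progress unscanned, so ITT should lead for OS, iPFS and ePFS

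*Combined protocol and SAP*

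**What the plan says.** SAP section 3.1 is the only text that assigns an analysis set to the secondary efficacy endpoints. The main efficacy analysis is to use both ITT and PP, "meanwhile the secondary efficacy endpoints will be analyzed using the PP population".

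The SAP admits a patient to PP if eligible and if the patient "had at least 2 valid tumor evaluations (baseline + 1st assessment"). Protocol 10.5 is similar: "having at least two valid tumour assessments (baseline and one evaluation MRI or CT-scan"), with no deviation that invalidates the primary endpoint. Protocol 5.3 sets the timing: "After 56 days of treatment, a contrast enhanced brain MRI and CT body scan will be performed as first tumour assessment".

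The survival clocks start earlier. Protocol 10.2: "OS is calculated as the time from date of inclusion to date of death due to any cause". SAP 4.6 has iPFS "defined as the time from inclusion (first dose of treatment) until intracranial tumour progression (RECIST 1.1) or death", and SAP 4.7 has ePFS "defined as the time from inclusion (first dose of treatment) until extracranial tumour progression (RECIST 1.1) or death".

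The shells do not follow section 3.1. The first OS shell is headed "4.5.1.ITT ALL PATIENTS: INTRACRANIAL OVERALL SURVIVAL (IOS"), and ITT and PP versions follow for OS, iPFS and ePFS, overall and by cohort.

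**The concern.** The one sentence that governs these endpoints points to PP, while the output is laid out for two sets. Either could be reported as the trial's survival result, and PP is the one the text supports.

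PP is a poor lead set for time-to-event endpoints here. Membership depends on reaching a scan after the clock has started, so a patient who dies before any scan is an event in ITT and absent from PP. Patients who progress clinically and never have the first scan are also left out of PP, and their later deaths go with them. Protocol 10.1 foresees both groups. In a single-arm trial no control arm carries the same selection, so a survival figure set beside outside data would look better for a reason unrelated to treatment.

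**Working it through.** **1. Text against shells**

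| Place | Endpoint | Set |
|---|---|---|
| SAP 3.1 (text) | Secondary efficacy | PP only |
| SAP 4.5.1–4.5.3 / 4.5.4–4.5.6 | OS | ITT / PP |
| SAP 4.6.1–4.6.3 / 4.6.4–4.6.6 | iPFS | ITT / PP |
| SAP 4.7.1–4.7.3 / 4.7.4–4.7.6 | ePFS | ITT / PP |
| SAP supplement 2.2, 2.3 | OS and iPFS by radiotherapy | ITT only |
| SAP 7.1, 7.2; supplement 2.4 | OS, iPFS, ePFS by symptomatic group | none named |

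Protocol 10.5 and the synopsis list the populations without ranking them.

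**2. The plan's own figure.** Protocol 10.1 uses rates of 40% and 60%, one-sided 5% and 80% power: n = [(1.645·√0.24 + 0.842·√0.24)/0.20]² = 37.1, so 38 evaluable. Then 38/0.80 = 47.5, so 48 enrolled. Both figures reproduce. The 20% allowance covers patients lost, dead or progressed without a first assessment, combined. No split is given.

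**3. Effect of unscanned deaths.** Let e be the share of ITT patients who die before any post-baseline scan, and suppose PP drops only these. After those deaths the number still alive is the same in both sets, but the PP denominator is smaller by the factor (1 − e):

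S_PP(t) = S_ITT(t) / (1 − e)

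The documents do not give e. I assume 0 to 20%, because the planned 20% mixes deaths with other reasons.

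| e | 0 | 5% | 10% | 15% | 20% |
|---|---|---|---|---|---|
| factor | 1.00 | 1.05 | 1.11 | 1.18 | 1.25 |

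Per patient: in cohort 2 (N = 15), one unscanned death gives 15/14 = 1.07 and two give 15/13 = 1.15. In cohort 1 (N = 48), one gives 48/47 = 1.02.

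**4. Illustration on OS.** Assume exponential OS with a 9-month median, the general figure in protocol 2.3. Day 56 is 1.84 months, and the share dead by then is 1 − 2^(−1.84/9) = 13.2%. The PP median is 9·log2(2/(1 − e)), and 12-month OS in ITT is 2^(−12/9) = 39.7%.

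| Early deaths unscanned | e | PP median OS (months) | PP 12-month OS |
|---|---|---|---|
| none | 0 | 9.0 | 39.7% |
| half | 6.6% | 9.9 | 42.5% |
| all | 13.2% | 10.8 | 45.7% |

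The last row is the ceiling under this illustration. I give no iPFS or ePFS equivalent.

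**5. What the formula leaves out.** Unscanned clinical progressors also drop out of PP. If, as expected, they die sooner than the rest, they widen the OS gap beyond 1/(1 − e). Exclusions for ineligibility, deviations or loss to follow-up can act in either direction.

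**6. iPFS in ITT.** Protocol 10.2 and SAP 4.6 both count death as an event. Protocol 10.2 also censors patients with no image after baseline on the day after inclusion, without restating that they must be alive. Read literally for a patient who dies unscanned, that rule would remove the event and carry the same bias into ITT.

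**The case against.** The strongest reply is that the output already deals with this. Every main OS, iPFS and ePFS result is laid out on ITT, ahead of PP, and SAP Tables 2, 4 and 7 list excluded patients with reasons. A reader will see any gap between the sets and its cause. These endpoints are descriptive and carry no success rule. The symptomatic-group tables are extra analyses asked for by the coordinator, and the supplement's baseline and radiotherapy tables for the same groups are already labelled ITT.

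Most of that stands, and it limits the consequence. It does not remove the defect: the stated rule still selects PP, and nothing tells the reader that the ITT tables lead.

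The size can also be challenged, and fairly. e may be zero. Extra scans are allowed at any time, and the protocol's PP definition accepts any one evaluation MRI or CT, so a death before day 56 need not be unscanned. The 9-month median is a general figure and not specific to this trial's eligibility. SAP 4.6.1 does report nobody censored at time 0 for want of assessments, but that concerns censoring and does not show that nobody died unscanned.

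A reader might infer that unscanned deaths are the only source of bias, since progression is judged on scans. Protocol 10.1 does not support that: it expects some patients to progress without the first assessment. A reader might also infer that the plan names no set at all for these endpoints. It does: section 3.1 names PP. The fault is that the shells disagree with it and that PP is the wrong lead.

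**Conclusion.** The concern holds. SAP 3.1 states a rule that conflicts with the SAP's own shells and, if followed, leaves out of the survival estimates patients who die or progress before a first scan. For those patients the push on reported survival is upward. For unscanned deaths alone it is a factor of 1.00 to 1.25 over an assumed e of 0 to 20%. The net difference between PP and ITT cannot be derived from the documents.

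It would go too far to say that ITT survival is unplanned, since those tables exist, or that the trial's conclusion is at risk. The success rule in protocol 4.1 rests on intracranial response before local treatment and does not use these endpoints. The point is worth correcting because the correction is nearly free and settles which survival figures count as the planned result.

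**What to change.** - In SAP 3.1, replace the clause "meanwhile the secondary efficacy endpoints will be analyzed using the PP population" with: *OS, iPFS and ePFS are analysed primarily in the ITT population; PP results are supportive.* The clause must be replaced, because a sentence added beside it would leave the conflict in place.
- Label the symptomatic-group survival shells (SAP 7.1 and 7.2, supplement 2.4) as ITT, matching supplement 2.2 and 2.3.
- As a clarification in protocol 10.2, state: *A death before any post-baseline image is an iPFS event at the date of death; only patients alive with no post-baseline image are censored the day after inclusion.*

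The change is deliberately limited to these three endpoints, so the response-rate analysis, which is sized on 38 evaluable patients, stays as it is. Response duration, already shown on both sets in SAP Tables 43 and 44, concerns responders only, and they all have a scan.

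The cost is two sentences and a set label on a few shells. The main ITT tables are already planned and no new data are needed. The downside is that the leading survival figures may be slightly less favourable.
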